#### 3.3 Other Efficacy Endpoints

The following additional efficacy endpoints will be evaluated for Part 1:

[figure not shown]
- The achievement of response in IBDQ Bowel Symptom domain (defined as increase of IBDQ bowel symptom domain score ≥ 6 from Baseline) at Week 8;
- The achievement of response in IBDQ fatigue item (defined as increase of IBDQ fatigue item score ≥ 1 from Baseline) at Week 8;
- The achievement of SFS of 0, RBS of 0 and endoscopic subscore of 0 at Week 8;
- The achievement of SFS of 0, RBS of 0 and endoscopic subscore of ≤ 1 at Week 8;
- The achievement of clinical remission per Full Mayo score at Week 8;
- Change in Full Mayo score from Baseline at Week 8;
- The achievement of clinical remission per Partial Mayo score over time;
- The achievement of clinical response per Partial Adapted Mayo score over time;
- The achievement of clinical response per Partial Mayo score over time;
- The achievement of SFS  $\leq$  1 over time;
- The achievement of RBS of 0 over time;
- The achievement of Fecal calprotectin below 150 mg/kg over time;
- Change from Baseline in fecal calprotectin over time;
- Change from Baseline in hs-CRP over time;
- Change from Baseline in Partial Adapted Mayo score, Partial Mayo score and SFS, RBS over time;
- Change from Baseline in UCEIS score over time;
- Change from Baseline in laboratory and nutritional parameters (e.g., hemoglobin, hematocrit, albumin, total protein concentration, and weight);
- Change from Baseline in subject-reported stool frequency (absolute values) over time;
- Change from Baseline in IBDQ total and domain score over time;
- Change from Baseline in individual IBDQ item under Bowel Symptom domain (for Q1, Q5, Q9, Q13, Q17, Q20, Q22, Q24, Q26, and Q29) over time;

- The achievement of IBDQ response (defined as increase of IBDQ total score
   ≥ 16 from Baseline) over time;
- The achievement of IBDQ remission (defined as IBDQ total score ≥ 170) over time;
- Change from Baseline in EQ-5D-5L score over time;
- Change from Baseline in WPAI scores over time;
- Change from Baseline in SF-36 Physical Component Summary (PCS) and Mental Component Summary (MCS) components and domain scores over time;
- Summary of PGIC improvement category over time;
- Summary of PGIS severity category over time;
- Change from Baseline in FACIT-F score over time;
- Change from Baseline in UC-SQ score over time;
- UC-related hospitalizations through Week 8;
- UC-related surgeries through Week 8;
- All-cause hospitalizations through Week 8;
- All-cause surgeries through Week 8.

The following additional efficacy endpoints will be evaluated for Part 2:

- The achievement of clinical remission per Adapted Mayo score at Week 16;
- The achievement of endoscopic improvement at Week 16;
- The achievement of endoscopic remission at Week 16;
- The achievement of clinical response per Adapted Mayo score at Week 16;
- The achievement of clinical response per Partial Adapted Mayo score at Week 10;
- The achievement of histologic-endoscopic mucosal improvement at Week 16;
- The achievement of no bowel urgency at Week 16;
- The achievement of no abdominal pain at Week 16;
- The achievement of histologic improvement at Week 16;
- Change from Baseline in IBDQ total score at Week 16;

- The achievement of mucosal healing at Week 16;
- Change from Baseline in FACIT-F score at Week 16.

## 3.4 Safety Endpoints

The following endpoints will be included in the safety analyses:

- Treatment emergent adverse events (TEAEs);
- Serious adverse events (SAEs);
- Adverse events of special interest (AESIs);
- Adverse events (AEs) leading to discontinuation of study drug;
- Vital signs and laboratory tests.

## 4.0 Analysis Populations

[figure not shown]
Significant non-compliance was identified at a site (Investigator ID 527969). As a result of this finding, efficacy data for the subjects enrolled at this investigational site will be excluded from the statistical analyses. Safety data for those subjects will be included in the statistical analyses. There were 6 subjects enrolled at this site in this study.

#### **Intent-to-Treat (ITT) Populations**

The ITT population for the 8-week DB induction period (Part 1) (denoted by **ITT1**) includes all randomized subjects who received at least one dose of double-blinded study drug in Part 1. The ITT1 population will be used for all efficacy and baseline analyses for Part 1.

The ITT population for the 8-week OL extended treatment period (Part 2) (denoted by ITT2) includes all subjects who received at least one dose of upadacitinib 45 mg QD in Part 2.

For ITT1 population, subjects will be included in the analysis according to the treatment groups that they are randomized to.

#### **Safety Populations**

The safety population for Part 1 (denoted by **SA1**) includes all randomized subjects who received at least one dose of study drug in Part 1.

The safety population for Part 2 (denoted by **SA2**) includes all subjects who received at least one dose of the upadacitinib 45 mg QD in Part 2.

The all upadacitinib treated safety population (denoted by **SA-UPA**) includes all subjects who received at least one dose of upadacitinib in Part 1 or Part 2.

[figure not shown]
For the safety populations, subjects are assigned to a treatment group based on the "as treated" treatment group, regardless of the treatment randomized. The "as treated" will be determined by the most frequent dose regimen received in the analysis period.

## 5.0 Subject Disposition

A summary of subject accountability will be provided where the number of subjects in each of the following categories will be summarized for each treatment group:

- Subjects randomized in Part 1;
- Subjects who took at least one dose of study drug (Part 1 and Part 2);
- Subjects who completed protocol-specified treatment (Part 1 and Part 2);
- Subjects who prematurely discontinued study drug (Part 1 and Part 2);
- Subjects who prematurely discontinued from study.

Number and percentage of subjects who discontinued study drug and who withdrew from the study will be summarized by reason (primary reason and all reasons) for each treatment group within Part 1 and Part 2. Subjects with multiple reasons for premature discontinuation will be counted once in the calculation of the number and percentage of total discontinuations.

## 6.0 Study Drug Duration and Compliance

For the safety populations (SA1 and SA2), duration of treatment will be summarized for each treatment group. Duration of treatment is defined for each subject as last dose date minus first dose date + 1. Duration of treatment will be summarized using the number of subjects treated, mean, standard deviation, median, minimum and maximum. In addition, the number and percentage of subjects in each treatment duration interval ( $\ge 2$  weeks,  $\ge 4$  weeks,  $\ge 6$  weeks,  $\ge 8$  weeks) will be summarized.

Treatment compliance will be summarized for each treatment period by treatment group. Treatment compliance is defined as the number of tablets actually taken divided by the number of tablets that should have been taken. Percent compliance will be summarized.

# 7.0 Demographics, Baseline Characteristics, Medical History, and Prior/Concomitant Medications

Demographics, Baseline or disease characteristics, medical history, and prior and concomitant medications will be summarized for the ITT1 population overall and by treatment group. Categorical variables will be summarized with the number and percentage of subjects; percentages will be calculated based on the number of non-missing observations. Continuous variables will be summarized with descriptive statistics (number of non-missing observations, mean and standard deviation, median, minimum and maximum).

#### 7.1 Demographics and Baseline Characteristics

Continuous demographic variables include age, weight, height, and body mass index (BMI). Categorical demographic variables include:

- Sex (Male, Female)
- Age Group 1 (< 18 year,  $\geq$  18 years < 40 years,  $\geq$  40 years < 65 years,  $\geq$  65 years)
- Age Group 2 ( $\leq$  median, > median)

#### Upadacitinib (ABT-494) M14-675 – Statistical Analysis Plan Version 6.0 – 19 January 2021

- Weight Group ( $\leq$  median, > median)
- BMI Group (normal:  $< 25 \text{ kg/m}^2$ , overweight:  $\ge 25 30 \text{ kg/m}^2$ , obese:  $\ge 30 \text{ kg/m}^2$ )
- Ethnicity (Hispanic or Latino, not Hispanic or Latino)
- Race (White, Black/African American, American Indian/Alaska Native, Native Hawaiian or Other Pacific Islander, Asian, Other)
- Region (US, ex-US)
- Tobacco user (current, former, never, unknown)
- Alcohol user (current, former, never, unknown)

#### Continuous baseline or disease characteristics variables include:

- Weight (kg)
- Height (cm)
- BMI  $(kg/m^2)$
- Disease duration (years)
- Full Mayo score and its components (stool frequency, rectal bleeding, Physician Global Assessment, and endoscopy subscores)
- Partial Mayo score
- Adapted Mayo score
- hs-CRP (mg/L)
- Fecal Calprotectin (μg/g)
- IBDQ total and domain score
- Short Form 36 Health Survey (SF-36) and its components
- European Quality of Life 5 Dimensions 5 Levels (EQ-5D-5L)
- Functional Assessment of Chronic Illness Therapy-Fatigue (FACIT-F)
- WPAI and its components
- Ulcerative Colitis Symptoms Questionnaire (UC-SQ)

Categorical baseline or disease characteristics variables include:

[figure not shown]
- Bio-IR status (Bio-IR, non-Bio-IR),
- Prior exposure to biologic therapy (yes, no) for non-Bio-IR
- Number of prior biologic treatments ( $\leq 1$  or > 1) for Bio-IR
- Prior exposure to anti-TNF (yes, no)
- Baseline corticosteroid use (yes, no)
- Baseline immunosuppressant use (yes, no)
- Baseline aminosalicylates use (yes, no)
- Baseline Adapted Mayo score ( $\leq 7, \geq 7$ )
- Baseline Full Mayo score ( $\leq 9, > 9$ )
- Baseline hs-CRP ( $\leq 5 \text{ mg/L}$  and > 5 mg/L)
- Disease duration Group 1 ( $\leq$  3 years, > 3 years)
- Disease duration Group 2 ( $\leq$  median, > median)
- Disease extent (rectosigmoid, left-sided, extensive/pancolitis)

#### 7.2 Medical History

Medical history data will be coded using the Medical Dictionary for Regulatory Activities (MedDRA). The actual version of the MedDRA coding dictionary will be noted in the statistical tables and clinical study report. The number and percentage of subjects in each medical history category (by MedDRA system organ class and preferred term) will be summarized overall and by treatment group. The system organ class (SOC) will be presented in alphabetical order, and the preferred terms will be presented in alphabetical order within each SOC. Subjects reporting more than one condition/diagnosis will be counted only once in each row (SOC or preferred term).

#### 7.3 Prior and Concomitant Medications

Prior and concomitant medications will be summarized by generic name (ITT1 population for prior medication; ITT1 and ITT2 populations for concomitant medications). A prior medication is defined as any medication taken prior to the date of the first dose of study

drug in Part 1. A concomitant medication is defined as any medication that started prior to the date of the first dose of study drug and continued to be taken after the first dose of study drug or any medication that started on or after the date of the first dose of study drug, but not after the date of the last dose of study drug + 1 day. The number and percentage of subjects taking medications will be summarized by generic drug name based on the World Health Organization (WHO) Drug Dictionary for both prior and concomitant medications.

#### 8.0 Efficacy Analyses

[figure not shown]
#### 8.1 General Considerations

The efficacy analyses for the 8-week DB induction period (Part 1) will be conducted in the ITT1 population. The efficacy analyses for the 8-week OL extended treatment period (Part 2) will be conducted in the ITT2 population. All tests will be at the  $\alpha$  level of 0.05 (2-sided). "Baseline" refers to the last non-missing observation prior to the first administration of the study drug or prior to the randomization if no study drug is given.

Unless otherwise specified, categorical variables will be analyzed using Cochran-Mantel-Haenszel (CMH) test, stratified by bio-IR status (bio-IR vs. non-bio-IR), Baseline corticosteroid use (yes vs. no) and Baseline Adapted Mayo score (≤ 7 vs. > 7). Any subject who was randomized under the wrong stratum will be analyzed according to the actual stratum the subject belongs to. Continuous variables collected longitudinally will be analyzed using Mixed-Effect Model Repeat Measurement (MMRM) method. Continuous variables collected at only one post-baseline visit (such as Mayo score) will be analyzed using an Analysis of Covariance (ANCOVA) model.

#### 8.2 Handling of Potential Intercurrent Events

Potential intercurrent events considered in the Induction Study include 1) premature discontinuation of study drug and 2) initiation or dose escalation of UC-related corticosteroids defined in Section 8.2.2. Intercurrent events will be handled using the following methods for the efficacy analysis:

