Corticosteroids are used in patients with more severe symptoms but are not useful for longer term therapy.⁶ The frequency and severity of corticosteroid toxicities are significant, including infections, emotional and psychiatric disturbances, skin injury, and metabolic bone disease. Corticosteroids are not effective for the maintenance of remission and the UC practice guidelines from the American College of Gastroenterology recommend against chronic steroid treatment.⁷ Patients with moderate to severe symptoms may derive some benefits from immunomodulatory agents (azathioprine [AZA], 6-mercaptopurine [6-MP], or methotrexate [MTX]); however, the use of these agents is limited as induction treatment due to a slow onset of action (3 to 6 months) and as maintenance therapy due to adverse events (AEs), including bone marrow suppression, infections, hepatotoxicity, pancreatitis, and malignancies.^{7,8} Despite these therapies, approximately 15% of UC patients experience a severe clinical course, and 30% of these patients require removal of the colon/rectum, to eliminate the source of the inflammatory process, although accompanied by significant morbidity.^{9,10}

Biological agents targeting specific immunological pathways have been evaluated for their therapeutic effect in treating patients with UC. Anti-tumor necrosis factor (TNF) agents were the first biologics to be used for IBD. Infliximab, adalimumab, and golimumab are successfully being used for the treatment of UC. Vedolizumab, an anti-adhesion therapy, has been approved for the treatment of IBD.

Anti-TNF therapies are an effective treatment for patients who are steroid refractory or steroid dependent, who had inadequate response to a thiopurine, or who are intolerant to these medications. Potential risks with anti-TNF therapies include infusion or injection site reactions, serious infections, lymphoma, heart failure, lupus-like syndromes, and demyelinating conditions.¹¹ Despite the beneficial results achieved with the available biologic agents, only 17% to 45% of patients who receive them are able to achieve clinical remission.¹²⁻¹⁵ Thus, there remains a clear medical need for additional therapeutic options in UC for patients with inadequate response to or intolerance to conventional therapies and biologic therapies.

Rationale for Development of a JAK Inhibitor in UC

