In order to minimize missing data for efficacy and safety assessments, subjects who prematurely discontinue study drug treatment should continue to be followed for all regularly scheduled visits, as outline in the Activity Schedule, unless they have decided to discontinue the study participation entirely (withdrawal of informed consent). Subjects should be advised on the continued scientific importance of their data even if they discontinue treatment with study drug early.

If a subject prematurely discontinues study participation (withdrawal of informed consent), the procedures outlined for the Premature Discontinuation Visit must be completed as soon as possible, preferably within 2 weeks.

A final telephone visit will occur for all subjects, approximately 30 days after the last dose of study medication to determine the status of any ongoing AEs/serious AEs (SAEs) or the occurrence of any new AEs/SAEs.

All attempts must be made to determine the date of the last study drug dose and the primary reason for premature discontinuation or study participation. The information will be recorded on the appropriate eCRF page. However, these procedures should not interfere with the initiation of any new treatments or therapeutic modalities that the investigator feels are necessary to treat the subject's condition. Following discontinuation

of the study drug, the subject will be treated in accordance with the investigator's best clinical judgment, irrespective of whether the subject decides to continue participation in the study.

For subjects that are considered lost to follow-up, reasonable attempts must be made to obtain information on the final status of the subject. At a minimum, two phone calls must be attempted and one certified letter must be sent and documented in the subject's source documentation.

Subjects who discontinue the study prematurely will not be replaced.

COVID-19 Pandemic-Related Acceptable Protocol Modification

During the COVID-19 pandemic, it has been necessary to employ mitigation strategies to enable the investigator to ensure subject safety and continuity of care. Acceptable mitigation strategies are identified and included in Section 5.3.1.1 and [Appendix C](#).

The investigator should contact the sponsor medical contact before discontinuing a subject from the study for a reason other than "planned per protocol," to ensure all acceptable mitigation steps have been explored.

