6.1.7 Toxicity Management

The toxicity management of the AEs including AEs of special interest consists of safety monitoring (review of AEs on an ongoing basis, and periodic/ad hoc review of safety issues by an independent Data Monitoring Committee), and if applicable interruption of study drug dosing with appropriate clinical management and/or discontinuation of the subjects from study drug. The management of specific AEs and laboratory parameters is described below.

For subjects who discontinue study drug but continue study participation and are on standard of care therapies, these toxicity management requirements do not apply (including alerts from the central laboratory) and any intolerability to standard of care therapies should be managed by the prescribing physician.

Serious Infections: Subjects should be closely monitored for the development of signs and symptoms of infection during and after treatment with study drug. Study drug should be interrupted if a subject develops a serious infection. A subject who develops a new infection during treatment with study drug should undergo prompt diagnostic testing appropriate for an immunocompromised subject. As appropriate, antimicrobial therapy

should be initiated, and the subject should be closely monitored. Study drug may be restarted once the infection has been successfully treated. These subjects will continue to be clinically monitored and will be evaluated in the safety analyses.

Subjects who develop active tuberculosis must be permanently discontinued from study drug (refer to "TB Testing/TB Prophylaxis" under Section 5.3.1.1).

Herpes zoster: If a subject develops herpes zoster, consider temporarily interrupting study drug until the episode resolves.

Gastrointestinal Perforation: Subjects presenting with the onset of signs or symptoms of a gastrointestinal perforation should be evaluated promptly for early diagnosis and treatment. If the diagnosis of spontaneous gastrointestinal perforation is confirmed (other than appendicitis or mechanical injury), the subject must be permanently discontinued from study drug.

Cardiovascular Events: Subjects presenting with potential cardiovascular events including non-cardiac, non-CNS thrombotic and embolic events should be carefully monitored. These events will be reviewed and adjudicated by an independent Cardiovascular Adjudication Committee in a blinded manner.

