#### 8.2.1 Premature Discontinuation of Study Drug

Data collected will be used regardless of premature discontinuation of study drug.

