#### 8.2.2 UC-Related Corticosteroids

[figure not shown]
The UC-related corticosteroids intercurrent event is defined as follows.

- subjects not on UC-related corticosteroids (systemic or locally acting corticosteroids for UC) at Baseline who initiated UC-related corticosteroids during the Induction Study;
- subjects on UC-related systemic corticosteroids at Baseline who have dosages increased to greater than the prednisone equivalent dose of corticosteroid taken at Baseline, or initiation of any rectal corticosteroids during the Induction Study regardless of rectal corticosteroid dose;
- subjects on UC-related rectal corticosteroids at Baseline who have dosages increased to greater than the dose taken at Baseline, or initiation of any new type of rectal or any systemic corticosteroids during the Induction Study.

The time point of the UC-related corticosteroids intercurrent event is defined as the date when one of the scenarios above occurs for a subject. As such, subjects will be considered as "non-responder" for binary endpoints at or after the occurrence of the UC-related corticosteroids intercurrent event through the end of the Induction Study. For continuous endpoints, all measurements at or after the occurrence of the UC-related corticosteroids intercurrent event through the end of the Induction Study will not be used in the analysis.

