# Appendix E. Attributes of the Estimand for Primary and Ranked Secondary Endpoints

	Attributes of the Estimand					
Estimand	Population	Endpoint	Treatment	Intercurrent Events	Statistical Summary	
Primary	ITT1 population (Subjects who were randomized and received at least one dose of study drug in Part1)	Achievement of clinical remission per Adapted Mayo score at Week 8	Upadacitinib 45 mg QD vs. placebo	IE1: premature discontinuation of study drug IE2: Initiation or dose escalation of UC-related corticosteroids  All data after IE1 will be used All subjects will be considered as non-responders at or after IE2	Difference in the percentage of subjects achieving clinical remission per Adapted Mayo score	
Categorical Key Secondary	ITT1 population	Achievement of Endoscopic improvement/Endoscopic remission/Adapted Mayo Score response/HEMI/no bowel urgency/no abdominal pain/histologic improvement/mucosal healing at Week 8  Partial Adapted Mayo Score response at Week 2	Upadacitinib 45 mg QD vs. placebo	IE1: premature discontinuation of study drug IE2: Initiation or dose escalation of UC-related corticosteroids  All data after IE1 will be used  All subjects will be considered as non-responders at or after IE2	Difference in the percentage of subjects achieving each binary secondary endpoint	
Continuous Key Secondary	ITT1 population	Change from Baseline in IBDQ total score/FACIT-F score at Week 8	Upadacitinib 45 mg QD vs. placebo	IE1: premature discontinuation of study drug IE2: Initiation or dose escalation of UC-related corticosteroids  All data after IE1 will be used  All Data after IE2 will not be used for continuous endpoints	Difference in mean change from Baseline in IBDQ total score and FACIT-F score	

In addition, a supplementary analysis will be conducted in which all data after IE1 and IE2 will be used for the primary and key binary secondary endpoints. This supplementary analysis corresponded to the AO analysis specified in Section 8.3.1 will provide additional insights into the understanding of the treatment effect.

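### Only corticosteroid rescue counts as non-response, so a Week 8 remission reached after any other UC rescue therapy counts as a remission for the randomised arm

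*SAP*

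**What the plan says.** SAP 8.2 names the intercurrent events as "1) premature discontinuation of study drug and 2) initiation or dose escalation of UC-related" corticosteroids, and Appendix E repeats the same two as IE1 and IE2.

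- **Stopping study drug (IE1).** SAP 8.2.1: "Data collected will be used regardless of premature discontinuation of study drug". Appendix E: "All data after IE1 will be used".
- **Corticosteroids (IE2).** Under SAP 8.2.2, subjects are non-responders "for binary endpoints at or after the occurrence of the UC-related corticosteroids intercurrent event through the end of the Induction Study"; for continuous endpoints, measurements from that point are dropped. Protocol 8.1.3 likewise has a failure rule for UC-related corticosteroids and for no other drug class.

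The protocol provides for subjects who are off drug but still assessed. Section 5.4.1 says that subjects who "prematurely discontinue study drug treatment should continue to be followed for all regularly scheduled visits", and that once drug is stopped "the subject will be treated in accordance with the investigator's best clinical judgment", whether or not they remain in the study. Section 6.1.7 has a clause that opens: "For subjects who discontinue study drug but continue study participation and are on standard of care therapies".

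Protocol 5.2.3.3 prohibits biologics, other JAK inhibitors, azathioprine and 6-MP, cyclosporine, tacrolimus, mycophenolate, thalidomide, rectal aminosalicylates and cytapheresis during the study. Section 7.0 makes receipt of prohibited treatment a reportable deviation. Neither section attaches an efficacy outcome to it.

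**The concern.** Take two placebo subjects who stop study drug at Week 2 and are in remission at Week 8. One was given prednisone and is a non-responder. The other was given infliximab and is a placebo remission. Protocol 5.2.3.3 bars starting systemic or rectal corticosteroids during induction just as it bars biologics, and the documents give no reason for scoring the two in opposite ways.

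The primary estimand is therefore a mixture: composite for corticosteroid rescue, treatment policy for every other rescue. It answers neither the question of remission whatever else was taken nor the question of remission without rescue. The same applies to the binary ranked secondary endpoints. For IBDQ and FACIT-F, scores after non-steroid rescue remain in the model.

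The gap is not confined to subjects who have stopped drug. Under Protocol 5.4.1, a prohibited medication forces discontinuation only if continuing study drug would place the subject at risk. Raising oral aminosalicylates, methotrexate or UC antibiotics above the Baseline dose is not an intercurrent event either, although Protocol 5.2.3.2 asks for stable doses.

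**Working it through.** **Step 1. Does any planned rule or analysis catch such a subject?** Take a subject with non-steroid rescue, no new or increased UC corticosteroid, and an observed Week 8 assessment.

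| Rule or analysis | What it acts on | Catches the subject? |
|---|---|---|
| Protocol 8.1.3 NRI | Leaving the study before the assessment | No |
| NRI-C, primary (SAP 8.3.1) | Missing evaluation, or corticosteroid event | No |
| NRI-NC | As NRI-C; changes only COVID-19 missingness | No |
| HMI | Subjects with no available measurements | No |
| AO, and the Appendix E supplementary analysis | Uses all values, even after corticosteroids | No; moves the other way |
| Deviation analysis (SAP 8.4.4) | Excludes subjects under a separate classification plan | Possibly, by exclusion and not as failure |
| MMRM (SAP 8.3.2) | Drops data only after the corticosteroid event | No |

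**Step 2. The plan's own figure.** Inputs from SAP 2.4: 5% against 18%, 154 against 308 subjects, two-sided Fisher's exact test, alpha 0.05. Exact enumeration gives 98.9% power and the normal approximation 98.8%. Both agree with the stated figure of more than 95%.

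**Step 3. What the gap could do.** The documents give no rescue rate, so every rate in this step is an assumption. Let f_P and f_U be the shares rescued without corticosteroids on placebo and upadacitinib, and g the chance that a rescued subject is in remission at Week 8. Take 5% and 18% as the rates with all rescue counted as failure. Then:

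- placebo rate = 0.05 + f_P × g
- upadacitinib rate = 0.18 + f_U × g
- extra remissions = 154 × f_P × g and 308 × f_U × g

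| f_P / f_U | g | Extra remissions, placebo / upadacitinib | Rates | Difference (points) | Power (Fisher) |
|---|---|---|---|---|---|
| 3% / 3% | 20% | 0.9 / 1.8 | 5.6% vs 18.6% | 13.0 | 98.5% |
| 2% / 1% | 20% | 0.6 / 0.6 | 5.4% vs 18.2% | 12.8 | 98.4% |
| 5% / 2% | 20% | 1.5 / 1.2 | 6.0% vs 18.4% | 12.4 | 97.4% |
| 10% / 3% | 30% | 4.6 / 2.8 | 8.0% vs 18.9% | 10.9 | 89.4% |
| 10% / 0% | 30% | 4.6 / 0 | 8.0% vs 18.0% | 10.0 | 84.4% |

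The direction depends on which arm is rescued more. With no placebo rescue, f_U = 3% and g = 20%, the upadacitinib rate is 0.18 + 0.03 × 0.20 = 18.6% and the difference is 18.6 − 5.0 = 13.6 points.

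For scale, 5% of 154 is 7.7 placebo remitters, so each misattributed one matters to the placebo rate.

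**The case against.** The strongest reply is that this is a declared choice. The estimand is defined regardless of drug discontinuation, and under treatment policy whatever is taken afterwards belongs to the outcome. Corticosteroids also have their own place in the protocol: they are permitted stable-dose background therapy, and starting them is singled out for discussion with the sponsor's medical director. This stands in part. The handling of IE1 is explicit. But treatment policy is suspended for one prohibited rescue class and kept for the others, without explanation, and nothing is said about non-steroid rescue while still on drug.

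Other points also carry weight. To matter, a subject must start rescue early, stay in follow-up, have the Week 8 endoscopy, take no new or increased UC corticosteroid, and remit. Open-label upadacitinib is available to Week 8 non-responders, which lowers the incentive for outside rescue. The SAP 8.4.4 analysis may remove some of these subjects. Its criteria are in a plan not included in the documents, so whether care given after stopping drug counts as a deviation is unresolved.

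Three stronger readings are tempting and not supported:

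- **A placebo inflation of 0.9 to 4.5 points.** A reader might assume 5% to 10% of placebo subjects rescued and apply the protocol introduction's figure for biologics, "only 17% to 45% of patients who receive them are able to achieve clinical remission": 0.05 × 0.17 = 0.9 points and 0.10 × 0.45 = 4.5 points. The rescue shares have no source, upadacitinib rescue is set to zero, and the remission range is background with no stated timepoint. With non-bio-IR held to 25% to 50%, half to three quarters of this population has already failed a biologic.
- **A false superiority claim.** If rescue is commoner on placebo, the gap shrinks the difference and works against the sponsor.
- **An intention that all rescue be failure.** The corticosteroid rule does not show this, and no section says it.

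**Conclusion.** The gap holds on the text. A Week 8 remission after non-corticosteroid UC rescue counts for the randomised arm in the primary, NRI-NC, HMI and AO analyses, and post-rescue IBDQ and FACIT-F scores stay in the MMRM. The only partial safeguard excludes subjects instead of scoring them.

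Its size is unknown and probably small over 8 weeks. The tabulated scenarios leave a difference of 13 down to 10 points. The sign is not fixed: more placebo rescue is conservative, more upadacitinib rescue inflates the effect. These results rest on assumed rescue and remission rates and on reading 5% and 18% as rates with all rescue failed. The rows with power below 95% therefore do not show that the trial is too small; at the design's own rates the stated power stands. What suffers is the interpretation of the estimate. The change should be made, but it is not a flaw that invalidates the trial.

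**What to change.** Before database lock and unblinding, add an intercurrent event to SAP 8.2 and Appendix E: start of any non-corticosteroid UC-directed therapy (the UC agents in Protocol 5.2.3.3), or escalation of background UC therapy above the Baseline dose, whether on or off study drug. Handle it as corticosteroids are handled: non-responder from the event onward for binary endpoints, later data not used for continuous endpoints. Report the current corticosteroid-only rule alongside.

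Timing matters. SAP Appendix D dates the last randomisation to 26 May 2020, so Week 8 fell around 21 July 2020, six months before SAP Version 6.0 of 19 January 2021. If the primary definition is kept for that reason, run the extended rule as a prespecified sensitivity analysis of the primary and ranked endpoints, and state why non-corticosteroid rescue is treated differently.

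Derive the event from all UC medication recorded through the Week 8 visit. The concomitant-medication definition in SAP 7.3 stops at last dose + 1 day and would miss most rescue started after discontinuation.

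The cost is a slightly more composite estimand, a few remitters in either arm becoming failures, and one small extra derivation. Protocol 5.2.3.2 already has medication changes assessed at each visit. This changes only how outcomes are scored, not how any subject is treated.
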